<sup>9FACT-G to be administered at visits during baseline, week 12, week 24 and week 36 assessments prior to MD encounter. Study team to check for completion of QOL data: more than 50% questions in each subscale, and at least 80% of questions overall in each questionnaire should be answered for the questionnaire to be considered complete.

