# 10.0 PATIENT REPORTED OUTCOMES (PROs – See Appendix #3)

#### 10.1 Quality of life (QOL) questionnaires

QOL questionnaires will be utilized to evaluate patient reported outcomes. This would include the Functional Assessment of Cancer Therapy- General (FACT-G) scale.

The Functional Assessment of Chronic Illness Therapy (FACIT) Measurement System is a collection of health-related quality of life (HRQOL) questionnaires targeted to the management of chronic illness [34]. The validated FACT-G scale is a 27-item compilation of general questions divided into four primary QOL domains: Physical Well-Being, Social/Family Well-Being, Emotional Well-Being, and Functional Well-Being. It is appropriate for use with patients with any form of cancer is widely used for assessing health-related QOL for different cancers. This questionnaire was designed for self-administration, written at 4th grade reading levels, and can be completed in 5-10 minutes [34]. A higher total score suggests well-being, and a lower score is an indication of inferior QOL.

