#### 10.2 Rationale

With the availability of several new targeted agents that prolong survival in mRCC, there is increasing emphasis on patient preferences based on treatment related quality of life. Two recent randomized trials, COMPARZ and PISCES (pending publication), demonstrated differences in QOL amongst sunitinib and its active comparator, pazopanib [19, 20]. The impact of treatment related toxicities on patients' QOL while receiving sunitinib on the 2/1 schedule is thus an important end-point of interest.

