#### 10.3 Data collection

QOL questionnaires will be administered at the initiation of treatment (baseline), and then at week 12, week 24 and week 36. These will be administered by the study team prior to patient encounters with the physician. The study team will also check for completion of all elements in each questionnaire, which will be collected from the patient at the end of that encounter. Only forms with more than 50% answers in each subscale will be considered acceptable. Moreover, at least 80% of questions overall in each questionnaire should be answered in order for it to be considered acceptable for analysis.

Missing data: Prorating subscale scores is acceptable as long as more than 50% of the items have been answered (e.g., a minimum of 4 of 7 items, 4 of 6 items, etc). The total (FACT-G) score is considered appropriate to score as long as overall item response rate is greater than 80% (e.g., at least 22 of 27 FACT-G items complete) [34].

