# Subsequent cycles – each visit at Day 42

- The assessment and evaluation in subsequent visits will include all the items enlisted in cycle 2 day 42, except:
- Restaging scans that will be performed every even numbered cycle (cycle 4, 6, etc.)
- QOL questionnaires will be assessed at baseline, week 12, week 24 and week 36 only.
- Biological correlate: Serum, plasma, buffy coat samples will be collected at at baseline, week 12, week 24, week 36, and at the time of disease progression.
- Bone scan will be repeated in patients with bone metastases at baseline or at the development of signs/symptoms consistent with bone metastases.
- CT/MRI brain will not need to be repeated unless a patient was to develop clinical symptoms that warrant brain imaging, in which case the decision to conduct CT versus MRI of the brain will be at the discretion of the treating physician.
- TSH will be checked in every even numbered cycle and additionally if clinically indicated.

• After 12 cycles, labs and follow-up visits may be allowed every 12 weeks instead of every 6 weeks if clinically indicated at the discretion of the treating physician.

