# **End of Treatment Visit**

- Physical Examination
- Weight
- Vital signs including: blood pressure, pulse and temperature
- Concomitant medications assessment including all current medications
- ECOG Performance Status
- Toxicity Assessment
- Laboratory Studies:

Complete Blood Count (CBC) with differential and platelets Serum Chemistries: albumin, alkaline phosphatase, total bilirubin, bicarbonate, BUN, calcium, chloride, creatinine, glucose, potassium, total protein, SGOT [AST], SGPT [ALT], sodium.

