#### 16.5 Analytic plan for secondary objectives:

- PFS will be measured from the date of initiation of treatment to the first of documented progression or death; and will be estimated using the Kaplan-Meier method. PFS is expected to be comparable to that seen with 4/2 (11 month median); however if the upper bound of the interval is less than 8 months this will be taken as an indication that the efficacy of 2/1 is inferior to that of 4/2.
- Toxicities will be tabulated by type and grade, and the incidence of all  $\geq$  grade 3 toxicities will be calculated by CTCAE v 4.03 along with a 95% confidence interval
- The percentage of patients who underwent one or more dose reductions, dose interruptions and/or treatment delays will be estimated along with a 95% confidence interval. The number of patients who discontinue treatment due to unacceptable toxicities will be recorded, and reported as a percentage of the total number of enrolled patients along with 95% confidence interval.
- Health-related quality of life (HRQOL) will be assessed by FACT-G questionnaires as a secondary endpoint. Questionnaires will be administered at baseline, week 12, week 24 and week 36. Descriptive summary statistics will be calculated for all continuous variables (means, standard deviations, medians, ranges, percentage of patients scoring in the highest category for each item) for the items in the subscales each time point. The mean trajectories of each group over time will be plotted for the total scores, along with scores for physical well-being, emotional well-being, functional well-being, and renal-specific scales for FACT-G.

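### FACT-G is not collected at the End of Treatment visit, so most patients who stop for toxicity between the fixed visits give no quality-of-life report around stopping

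*Combined protocol and SAP*

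**What the plan says.** Four places in the combined protocol and SAP give the same FACT-G schedule.

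- Section 3.2, calendar footnote: "FACT-G to be administered at visits during baseline, week 12, week 24 and week 36 assessments prior to MD encounter".
- Section 10.3: "QOL questionnaires will be administered at the initiation of treatment (baseline), and then at week 12, week 24 and week 36".
- Section 12.2, subsequent cycles: "QOL questionnaires will be assessed at baseline, week 12, week 24 and week 36 only".
- Section 16.5: "Questionnaires will be administered at baseline, week 12, week 24 and week 36".

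The FACT-G row of the calendar is marked at Cycle 1 Day 1 and in the even-cycle column, and is blank under End of Treatment and End of Study. In Section 12.2, the list headed "End of Treatment Visit" includes examination, performance status, toxicity assessment and laboratory tests, but no questionnaire. The 30-day follow-up list has none either.

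The plan does collect another measure when an event occurs. The calendar marks biological samples at End of Treatment, and Section 12.2 schedules them at "week 36, and at the time of disease progression".

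On purpose, Section 10.2 says: "The impact of treatment related toxicities on patients' QOL while receiving sunitinib on the 2/1 schedule is thus an important end-point of interest". Sections 10.4 and 16.5 plan descriptive summaries at each time point. The missing-data rule in Section 10.3 deals with unanswered items, not with patients who have stopped.

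**The concern.** Stopping for toxicity is the clearest case of toxicity affecting a patient's life, and it is the point at which no patient report is planned. The missing reports belong selectively to the patients who tolerated the 2/1 schedule least. The means at weeks 12, 24 and 36 therefore describe mainly those still on drug, and can look favourable partly because others have left. No analysis method recovers scores that were not collected.

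The scheduled forms already lean towards recovered states. They fall on Day 42, the end of an off-drug week on the starting schedule (Section 6.1), and the questionnaire asks about the past 7 days (Appendix 3). A reader of the final report could not tell how patients who gave up the drug for toxicity rated their quality of life at that time.

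**Working it through.** **1. The plan's own figure.** Section 16.3 states that 60 patients give a 95% confidence interval half-width below 10% at an observed composite toxicity rate of 10-15%. The Wald half-width is 1.96 × √(p(1−p)/60), which is 7.6 points at p = 0.10 and 9.0 points at p = 0.15. Exact intervals give 8.4 points (6/60) and 9.7 points (9/60). The figure reproduces. No design figure is given for FACT-G.

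**2. Inputs for the size of the gap.**

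- N = 60 (Section 16.3).
- Median PFS 11 months (Section 16.5), taken as exponential: hazard ln 2/11 = 0.0630 per month.
- Weeks 12 and 36 = 2.76 and 8.28 months.
- Probability r of stopping for toxicity by week 36 if that were the only reason to stop: **not in the documents**. Assumed 15%, range 10-20%, with constant hazard h = −ln(1−r)/8.28.

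**3. Toxicity stops with PFS events competing.** The probability of a toxicity stop by month t is h/(h + 0.0630) × [1 − exp(−(h + 0.0630)t)].

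| Assumed r | h per month | Stops by week 36 | of 60 | Stops before week 12 | of 60 |
|---|---|---|---|---|---|
| 10% | 0.0127 | 7.8% | 4.7 | 3.2% | 1.9 |
| 15% | 0.0196 | 11.8% | 7.1 | 4.8% | 2.9 |
| 20% | 0.0270 | 15.7% | 9.4 | 6.6% | 4.0 |

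**4. How many stops coincide with a form.** The visit window is ±5 days (Section 3.2). Around days 84, 168 and 252 this covers 33 of days 1-257, or 12.8%. If stops are spread evenly over days, 87.2% miss every window: 4.7 × 0.872 = 4.1, 7.1 × 0.872 = 6.2 and 9.4 × 0.872 = 8.2 patients. If stops are instead decided only at the six-weekly visits (weeks 6, 12, 18, 24, 30 and 36), equally often at each, three of the six carry a form. Half are then missed: about 2.4, 3.5 and 4.7 patients.

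**5. Why progression is left out of the count.** The same exponential gives 1 − exp(−0.0630 × 2.76) = 16.0% with a PFS event before week 12, or 9.6 of 60. These are not lost forms. The first restaging scan is at Cycle 2 Day 42 (2 × 6 = week 12), the same visit as the FACT-G, and the form is completed before the physician encounter. Restaging at Cycles 4 and 6 coincides with weeks 24 and 36 in the same way. Only early deaths, clinical deterioration or unscheduled scans would cost a form, and the documents give no rate for these.

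**The case against.** The strongest reply is that the schedule matches the endpoint. Section 16.2 defines it as change during treatment on schedule 2/1, so fixed on-treatment time points do not contradict the plan. The endpoint is secondary and descriptive, with no hypothesis, threshold or decision rule. Patients who stop for toxicity are not hidden: their percentage of all enrolled patients is reported with a 95% confidence interval, and toxicity is assessed at End of Treatment and at 30 days. All of this stands. It limits the weight of the point, but clinician grading does not replace the patient's own report.

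The reply also holds that an End of Treatment form may miss its target. Under Sections 6.3 and 7.0, a patient removed because toxicity did not recover may have been off drug for up to 4 weeks. The recall period is 7 days, and Section 12.2 gives no timing for the visit. This also stands, so such a form cannot be called the last on-treatment assessment. It still has value, because toxicity that fails to recover is by definition still present.

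A reader might infer three stronger things that the documents do not support:

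- **About 10 of 60 patients lose every post-baseline form through progression.** Restaging and FACT-G share the same visits.
- **Patients who stop for toxicity never report at stopping.** Some stops will coincide with a FACT-G visit. The documents also do not say whether forms continue after stopping, although follow-up then is 30 days for toxicity.
- **The plan claims that quality of life is preserved.** It makes no such claim.

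**Conclusion.** The gap is real and is one of data collection. Patients whose treatment ends for toxicity away from weeks 12, 24 and 36 have no planned quality-of-life report around stopping, and those who stop before week 12 have none after baseline.

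On an assumed 10-20% rate of stopping for toxicity, about 5-9 of 60 patients stop for this reason by week 36, about 2-4 of them before week 12. With stops spread evenly over days, about 4-8 would have no form near stopping. If stops were decided only at the six-weekly visits, the figure falls to about 2-5. These counts rest on the assumed rate, constant hazards and the plan's 11-month median PFS.

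The point affects the interpretation of a descriptive secondary endpoint only. It does not touch the primary endpoint or the sample size. The change is worth making because it is cheap and the data cannot be recovered afterwards.

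**What to change.** - **Sections 3.2 and 12.2:** add FACT-G to the End of Treatment column and the End of Treatment list for patients stopping at or before week 36, unless a form was completed at that same visit. Amend the word *only* in the quality-of-life line of Section 12.2 to match.
- **Section 16.5:** report these scores and their change from baseline descriptively, on a separate line, by reason for stopping (toxicity, progression, other), with days since last dose. Do not pool them into the week 12, 24 and 36 means or label them as on-treatment.

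**Cost:** a small amendment and, for patients stopping in that period, one questionnaire that Section 10.1 says "can be completed in 5-10 minutes", at a visit already planned. The forms will fall at unequal times, some will be completed off drug, and the toxicity group will be small, so the results support description only.

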#### 4.0 PATIENT SELECTION

#### 4.1 Inclusion Criteria

Patients must meet all of the following inclusion criteria to be eligible for enrollment:

- 1. Histologically or cytologically-confirmed metastatic renal cell carcinoma of clear cell histology. Prior nephrectomy is not a requirement for eligibility
- 2. Age  $\geq$ 18 years
- 3. Measurable or evaluable metastatic disease per RECIST v 1
- 4. ECOG performance status 0-1
- 5. Normal organ and bone marrow function as defined by:
  - Serum aspartate transaminase (AST; serum glutamic oxaloacetic transaminase [SGOT]) and serum alanine transaminase (ALT; serum glutamic pyruvic transaminase [SGPT]) ≤ 2.5 x laboratory upper limit of normal (ULN)
  - o Total serum bilirubin  $\leq 2.0 \text{ x ULN}$
  - Absolute neutrophil count (ANC)  $\geq 1500/\mu L$
  - o Platelets  $\geq 100,000/\mu L$
  - $\circ$  Hemoglobin  $\geq 9.0 \text{ g/dL}$  (transfusion permitted)
  - o Serum calcium ≤ 12.0 mg/dL
  - Serum creatinine  $\leq 2.5 \text{ mg/dL}$
- 6. Patients with a history of deep venous thromboembolism or pulmonary embolism on treatment with anticoagulation are eligible for the study.
- 7. Subjects must have the ability to understand and the willingness to sign a written informed consent document

#### 4.2 Exclusion Criteria

The presence of any of the following will exclude a patient from study enrollment.

- 1. Prior treatment with sunitinib or any other systemic therapy in the metastatic setting (prior neo/adjuvant therapy will be allowed if completed > 6 months prior to registration and therapy not discontinued for toxicity)
- 2. Uncontrolled hypertension (defined as blood pressure >140/90 mm Hg not controlled with anti-hypertensives)
- 3. Prior intraabdominal, intrathoracic, vascular, spinal or intracranial surgery or radiation therapy within 4 weeks of starting treatment
- 4. History of or known brain metastases, spinal cord compression, or carcinomatous meningitis
- 5. New York Heart Association (NYHA) grade II or greater congestive heart failure
- 6. Current treatment on another therapeutic clinical trial

<sup>h Labs and follow-up visits can be every 12 weeks after completion of 12 cycles, at the discretion of the treating physician

<sup>iEOS visit does not require CT scans if performed within the preceding 12 weeks.

<sup>1Biological correlates to include characterization of circulating DNA and tumor associated macrophages.

- 7. Any of the following within the preceding 6 months- myocardial infarction, severe/unstable angina, severe peripheral vascular disease (claudication) or procedure on peripheral vasculature, coronary/peripheral artery bypass, graft, cerebrovascular accident or transient ischemic attack, clinically significant bleeding
- 8. Pregnant or breastfeeding women are excluded from this study because there is an unknown, but potential risk for adverse events in nursing infants secondary to treatment of the mother with sunitinib. Breastfeeding must be discontinued if the mother is treated with sunitinib
- 9. Known human immunodeficiency virus (HIV) or acquired immunodeficiency syndrome (AIDS)-related illness
- 10. HIV-positive patients on combination antiretroviral therapy are ineligible because of the potential for pharmacokinetic interactions with sunitinib. In addition, these patients are at increased risk of lethal infections when treated with marrow suppressive therapy

#### 4.3 Inclusion of Women and Minorities

Both men and women and members of all races and ethnic groups are eligible for this trial.

#### 5.0 REGISTRATION

All patients will be registered in the approved Office of Research Administration (ORA) database at MD Anderson. For those subjects who are consented, but not enrolled, the reason for exclusion must be recorded. For registration procedures for this protocol, please refer to Section 15.2 of the protocol and the Multicenter Management Plan (Appendix D).

#### 6.0 TREATMENT PLAN

#### 6.1 Sunitinib Administration

Treatment will be administered on an outpatient basis. Sunitinib will be initially dosed at 50 mg by mouth daily (QD) for 2 weeks followed by a one week break. Cycles of treatment will be defined as 6 week intervals regardless of dosing interruptions. Thus patients will receive sunitinib during weeks 1, 2, 4 and 5 of each 6 week (42-day) cycle, with treatment breaks during weeks 3 and 6. Sunitinib will be given without regard to meals. Patients will record blood pressure measurements daily for the first week and at least once weekly thereafter throughout the course of treatment using blood pressure logs that will be provided to them [Appendix 2].

Patients who experience toxicity per Section 8 may undergo dose/schedule modification as indicated per section 7. Reported adverse events and potential risks of sunitinib are described in Section 8.0. Appropriate dose and schedule modifications for sunitinib are described in Section 7.0.

No investigational or commercial agents or therapies other than sunitinib may be administered with the intent to treat the patient's malignancy. The patient will be provided a

# Patient Pill Diary [Appendix 1] and instructed regarding its use to record each dose of oral medication.

# 6.2 General Concomitant Medications and Supportive Care Guidelines

Patients may receive Epogen/Procrit/Aranesp for anemia and a bisphosphonate for hypercalcemia and/or bone metastases as required. Anti-emetic therapy of any kind is permitted. Full transfusional support is permitted. The prophylactic use of growth factors is not allowed. The use of pyridoxine (vitamin B6) for the treatment of hand-foot syndrome is permitted. Palliative radiotherapy is allowed as long as there is no progressive disease per RECIST criteria; sunitinib may or may not be held during radiotherapy at the discretion of the treating physician. If held, dose changes must be recorded. No other approved or investigational anticancer treatment will be permitted during the study period, including chemotherapy, biological response modifiers, hormone therapy or immunotherapy. No other investigational drug may be used during treatment on this protocol, and concurrent participation in another clinical trial is not allowed.

Sunitinib is metabolized primarily by liver enzymes, in particular CYP3A4. Agents known to induce CYP3A4 including dexamethasone should be avoided. Agents known to inhibit this enzyme (e.g., grapefruit juice) should also be avoided. In particular, ketoconazole should be avoided if possible, since a clinical interaction study of sunitinib indicated that up to a 2-fold increase in plasma levels of sunitinib was induced by ketoconazole. In addition, concomitant treatment with the following drugs with dysrhythmic potential (ie, terfenadine, quinidine, procainamide, disopyramide, sotalol, probucol, bepridil, haloperidol, risperidone, and indapamide) is not recommended.

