#### 13.1.2 Disease Parameters

Measurable Disease Measurable lesions are defined as those that can be accurately measured in at least one dimension (longest diameter for non-nodal lesions and short axis for nodal lesions to be recorded) as  $\geq 20$  mm by chest x-ray, as  $\geq 10$  mm with CT scan, or  $\geq 10$  mm with calipers by clinical exam. All tumor measurements must be recorded in millimeters (or decimal fractions of centimeters).

Malignant lymph nodes To be considered pathologically enlarged and measurable, a lymph node must be  $\geq 15$  mm in short axis when assessed by CT scan (CT scan slice thickness recommended to be no greater than 5 mm). At baseline and in follow-up, only the short axis will be measured and followed.

Non-measurable disease All other lesions (or sites of disease), including small lesions (longest diameter < 10 mm or pathological lymph nodes with  $\ge 10$  to < 15 mm short axis) are considered non-measurable disease. Bone lesions, leptomeningeal disease, ascites, pleural/pericardial effusions, lymphangitis cutis/pulmonitis, inflammatory breast disease, and abdominal masses (not followed by CT or MRI) are considered as non-measurable.

Note: Cystic lesions that meet the criteria for radiographically defined simple cysts should not be considered as malignant lesions (neither measurable nor non-measurable) since they are, by definition, simple cysts.

'Cystic lesions' thought to represent cystic metastases can be considered as measurable lesions if they meet the definition of measurability described above. However, if non-cystic lesions are present in the same patient, these are preferred for selection as target lesions.

Target lesions All measurable lesions up to a maximum of 2 lesions per organ and 5 lesions in total, representative of all involved organs, should be identified as **target lesions** and recorded and measured at baseline. Target lesions should be selected on the basis of their size (lesions with the longest diameter), be representative of all involved organs, but in addition should be

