those that lend themselves to reproducible repeated measurements. It may be the case that, on occasion, the largest lesion does not lend itself to reproducible measurement in which circumstance, the next largest lesion which can be measured reproducible should be selected. A sum of the diameters (longest for non-nodal lesions, short axis for nodal lesions) for all target lesions will be calculated and reported as the baseline sum diameters. If lymph nodes are to be included in the sum, then only the short axis is added into the sum. The baseline sum diameters will be used as reference to further characterize any objective tumor regression in the measurable dimension of the disease.

Non-target lesions All other lesions (or sites of disease) including any measurable lesions over and above the 5 target lesions should be identified as **non-target lesions** and should also be recorded at baseline. Measurements of these lesions are not required, but the presence, absence, or in rare cases unequivocal progression of each should be noted throughout follow-up.

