## 13.1.4 Response Criteria

# 13.1.4.1 Evaluation of Target lesions

Response	Evaluation of Target Lesions
Complete Response	Disappearance of all target lesions. Any pathological
(CR)	lymph nodes (whether target or non-target) must have reduction in short axis to < 10 mm.
Partial Response	At least a 30% decrease in the sum of diameters of target lesions, taking as reference the baseline sum of
(PR)	diameters.
	At least a 20% increase in the sum of diameters of
	target lesions, taking as reference the smallest sum on study (this includes the baseline sum if that is the
Progressive Disease (PD)	smallest on study). In addition to the relative increase
(FD)	of 20%, the sum must also demonstrate an absolute
	increase of at least 5 mm.
	Note: the appearance of one or more new lesions is

	also considered progression.			
Stable Disease (SD)	Neither sufficient shrinkage to qualify for PR nor sufficient increase to qualify for PD, taking as reference the smallest sum diameters while on study.			

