# 16.2 Definition of secondary outcomes/endpoints:

- Progression-free survival (PFS) defined as the time from treatment initiation to disease progression using RECIST v 1 or death.
- Incidence of all ≥grade 3 toxicities per CTCAE version 4.03 criteria, defined as the percentage of patients who experience any grade 3 or greater toxicity that is possibly, probably, or definitely related to study therapy.
- Dose reductions, dose interruptions, dose delays will be recorded using pill diaries
  maintained by patients that will be reviewed and recorded at each visit. This outcome will be
  reported as the percentage of patients who underwent one or more dose reductions, dose
  interruptions and/or treatment delays. The number of patients who discontinue treatment due
  to unacceptable toxicities will be recorded, and reported as a percentage of the total number
  of enrolled patients.
- Changes in the patient reported outcomes in FACT-G (general) scale during treatment on schedule 2/1
- Changes in circulating DNA levels with antiangiogenic treatment
- Correlation of tumor associated macrophages (TAM) with response to therapy

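### The plan permits on-study palliative radiotherapy but has no rule for reading an irradiated target lesion, so radiation shrinkage enters the RECIST sum by default and can misclassify response or progression

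*Combined protocol and SAP*

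**What the plan says.** **Radiotherapy.** Section 6.2: "Palliative radiotherapy is allowed as long as there is no progressive disease per RECIST criteria". The section does not restrict which lesions may be treated. The only recording it asks for concerns sunitinib: "If held, dose changes must be recorded". The form list in Section 15.1 has no item for the site of radiotherapy.

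**The sum.** Under Section 13.1.2, target lesions are "All measurable lesions up to a maximum of 2 lesions per organ and 5 lesions in total", and a sum of diameters "for all target lesions will be calculated and reported as the baseline sum diameters". Section 13.1.4.1 defines partial response as "At least a 30% decrease in the sum of diameters of target lesions" against baseline. Progression needs "At least a 20% increase in the sum of diameters of" the target lesions over the smallest sum on study, and at least 5 mm in absolute terms. Section 13.1.4.3 takes the best response recorded at any time up to progression. None of these sections mentions an irradiated lesion.

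**PFS.** Section 16.2: "Progression-free survival (PFS) defined as the time from treatment initiation to disease progression using RECIST v 1 or death". Sections 13.1.6 and 16.5 agree and give no event, censoring or sensitivity rule for radiotherapy. Section 16.5 expects a median of 11 months and reads an upper confidence limit below 8 months as a sign that the 2/1 schedule is inferior. Section 13.1 sets scans every 12 weeks.

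**The concern.** The no-progression condition in Section 6.2 governs when radiotherapy may be given. It does not govern how later scans are read. If a target lesion lies in the field and shrinks because of radiation, the stated rules credit that shrinkage to the overall sum. Three things can follow: a partial response that owes nothing to sunitinib, growth in untreated lesions offset so that the 20% threshold is missed, or a lower nadir that changes the threshold for every later scan.

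PFS is at stake. It is the only efficacy endpoint with a decision rule, in a single-arm trial with no PFS sizing. A later call of progression makes the 8-month flag less likely. Because no form expressly captures the irradiated site, analysts could not reliably repair the reading afterwards.

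**Working it through.** **The plan's own figure.** The only sizing figure is for toxicity (Section 16.3): 60 patients, 95% half-width below 10% at a rate of 10-15%. The Wald half-width is 1.96 × √(p(1−p)/60), which is 7.6% at p = 0.10 and 9.0% at p = 0.15. The figure reproduces and this point does not affect it. There is no PFS figure to reproduce.

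**Inputs.** From Section 13.1.4.1: partial response at −30% from baseline, progression at +20% from the smallest sum with at least +5 mm. Lesion sizes and the amount of radiation shrinkage below are assumptions.

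**Effect on progression.** Baseline sum 100 mm: one 40 mm lesion, other lesions totalling 60 mm. Radiation takes the 40 mm lesion to 20 mm.

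| Reading | Sum at which progression is called | Other lesions at that point | Growth needed in other lesions |
|---|---|---|---|
| Irradiated lesion left out | 60 × 1.2 = 72 mm | 72 mm | +12 mm (20%) |
| Kept, shrinkage seen first (nadir 20 + 60 = 80) | 80 × 1.2 = 96 mm | 96 − 20 = 76 mm | +16 mm (27%) |
| Kept, both changes in one 12-week interval | 100 × 1.2 = 120 mm | 120 − 20 = 100 mm | +40 mm (67%) |
| No radiotherapy, 40 mm lesion stable | 100 × 1.2 = 120 mm | 120 − 40 = 80 mm | +20 mm (33%) |

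Judged against the lesion left out, both kept readings delay progression. Judged against no radiotherapy at all, the nadir reset brings it forward (76 mm instead of 80 mm). Regrowth can do the same: with the other lesions stable at 60 mm, the irradiated lesion reaches progression at 96 − 60 = 36 mm, still below its own 40 mm baseline.

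**Changes of category.**
- Targets 50 + 50 mm, irradiated lesion to 30, other to 65. Kept: 95/100 = −5%, stable. Left out: 65/50 = +30% and +15 mm, progression.
- Targets 60 + 40 mm, irradiated lesion halved to 30, other unchanged. Kept: 70/100 = −30%, partial response. Left out: 40/40 = 0%, stable. The 12-week confirmatory scan in Section 13.1 does not prevent this if the shrinkage lasts.

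**Effect on the 8-month rule.** This is an illustrative simulation: 60 patients, exponential PFS, all with events, no censoring, two-sided 95% log-log interval for the Kaplan-Meier median, 4,000 runs. Section 16.5 does not state the interval's level, so 95% is assumed. A share of patients has PFS lengthened by one scan interval (84/30.4375 = 2.76 months).

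| True median | Share delayed | Chance that the flag fires | Typical observed median |
|---|---|---|---|
| 5 months | 0 / 5 / 10% | 78 / 72 / 69% | 5.0 / 5.2 / 5.3 months |
| 6 months | 0 / 5 / 10% | 37 / 32 / 28% | 6.0 / 6.2 / 6.3 months |

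The documents give no radiotherapy frequency. At an assumed 5-15%, 3 to 9 of 60 patients are irradiated. Only those with a target lesion in the field can be affected, and fewer still would have progression masked. A delayed share of 10% (6 patients) is therefore probably too high, and 5% (3 patients) is already generous at the lower end of that range. The simulation also applies delay only, never the earlier progression shown above.

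**The case against.** **The documents do not say that irradiated lesions stay in the sum.** A reader might infer an instruction to keep them. Section 13.1 adopts a published RECIST guideline that is not reproduced in full, and whether it covers lesions treated on study cannot be seen from the documents. This stands: inclusion is the default result of summing all target lesions with no stated exception, not an express rule. It does not remove the gap, because Section 13 is what sites will follow.

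**Several provisions limit the effect.** Bone lesions are non-measurable (Section 13.1.2), so bone radiotherapy cannot shrink the sum. Known brain metastases are excluded (Section 4.2), and a new brain lesion is itself progression. New lesions and unequivocal non-target progression count whatever the target sum (Sections 13.1.4.1 to 13.1.4.3). Section 6.1 bars treatment other than sunitinib given with intent to treat the malignancy. All of this stands and keeps the number affected small. None of it stops a palliative field from covering a soft-tissue target lesion.

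**Later reconstruction may be possible.** Section 15.1 collects cycle-by-cycle treatment forms, disease measurements and source documents, and the lead principal investigator arbitrates response (Section 15.0). This helps in part, but none of these expressly captures the irradiated site.

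**Counting radiotherapy as a PFS event treats symptom control as progression.** This is fair, and it is why such an analysis should only be supportive.

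**Conclusion.** The gap is real and minor. The stated rules let radiation shrinkage of a target lesion turn progression into stable disease, or stable disease into partial response, and the plan has neither a reading rule nor a record of the site to correct it. The size cannot be fixed from the documents: it depends on an unstated radiotherapy frequency and on assumed lesion sizes. On the illustration above, a 5% delayed share lowers the chance of the PFS flag by about 5 percentage points and moves the median by about 0.2 months. The primary toxicity endpoint and the sample size are unaffected.

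Two stronger readings are tempting and not supported. One is that PFS will be lengthened. Later progression is the likely net effect, but a nadir reset or regrowth of the irradiated lesion can bring progression forward. The other is that the tumor-associated macrophage analysis is contaminated through best overall response. Section 16.2 refers only to response to therapy, Section 11.2 to clinical outcome, and Section 16.5 specifies no such analysis. Response rate is not a listed endpoint.

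**What to change.** - **Reading rule (Sections 13.1.2 and 13.1.4).** From the date of on-study radiotherapy, leave the irradiated lesion out of the target sum and recompute the baseline, nadir and current sums without it. Follow it as a non-target lesion, where only unequivocal progression counts. If it was the only target lesion, assess by the non-target and new-lesion rules.
- **Recording.** Capture the site and date of radiotherapy and whether a target lesion was in the field.
- **Analysis (Section 16.5).** Add one supportive PFS sensitivity analysis for patients irradiated before progression, for example counting first on-study radiotherapy as an event. Leave the main PFS definition unchanged.

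This concerns measurement and analysis only. It does not touch whether radiotherapy is permitted. The cost is a short addition to Sections 13 and 16.5 and a small addition to the case report form, with no extra scans or patients. The downside is fewer target lesions in a few patients. The site and date are best captured prospectively, and the rule should be settled before PFS is analysed.
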